##### Exploratory Objectives

The exploratory objectives are to define:

- Determination of response associated clinical characteristics,
- The incidence of activating mutations in MTOR and related genes in patients who respond to TAK228 in their archival lymphoma biopsy tissue,
- The change in phosphorylation of mTORC1/2 target proteins and related signaling proteins at baseline and after therapy with TAK228 in peripheral blood mononuclear cells by utilizing reverse phase protein array,
- The change in phosphorylation of mTORC1/2 target proteins and related signaling proteins at baseline and after therapy with TAK228 in optional pre- and post- therapy biopsy by utilizing reverse phase protein array

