It is currently difficult to predict which patients will have response to mTOR pathway directed therapies due to lack of actionable biomarkers. It is possible to assess for the activity of mTOR inhibition by evaluation of phosphorylation of downstream targets of mTOR, such as S6K and 4EBP1. To evaluate the baseline phosphorylation and effect of TAK228 on these markers, we propose to collect peripheral blood mononuclear cells and archival tissue blocks from patients enrolled on trial for correlative studies. The peripheral blood mononuclear cells will be evaluated as a surrogate for mTORC1/2 inhibition and Akt phosphorylation after exposure to TAK228 via reverse phase protein array (RPPA). For the list of the 217 currently utilized antibodies in the MD Anderson RPPA platform. Archival tumor blocks will be stored for attempted correlation of clinical responders vs non-responders with genomic assessment.

It has recently been reported that mutations of the MTOR may activate the pathway and thus predict clinical response to mTOR inhibitors. Patients with available archival tissue will undergo an evaluation for the presence of an MTOR mutation which could serve as a potential biomarker in future clinical trials.

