**Proposed Treatment/Study Plan:**

Is treatment assignment randomized?  Yes  No

Is this a blinded or double-blinded study?  Yes  No

TAK228 milled API will be administered once daily at approximately the same time on each scheduled dosing day and not to take more than the prescribed dose at any time. It is recommended that each dose of TAK228 be given orally with 8 ounces (240 mL) of water. TAK228 should be administered on an empty stomach, and patients should be instructed to refrain from eating or drinking (aside from water and prescribed medications) for 2 hours before and 1 hour after each dose. Cycles are repeated every 28 days.

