### **Screening Evaluation**

A history and physical examination, including performance status evaluation, height, weight, and vital signs, should be performed within 28 days prior to the first dose of TAK228.

The following laboratory studies should be performed within 3 days prior to the first dose of TAK228 – CBC with differential, Serum chemistries – sodium (Na), potassium (K), chloride (Cl), glucose, bicarbonate (CO2), blood urea nitrogen (BUN), creatinine (Cr), calcium (Ca), magnesium (Mg), phosphorus, total protein, albumin, alkaline phosphatase, aspartate transaminase (AST), alanine transaminase (ALT), total bilirubin, direct bilirubin, uric acid, lactate dehydrogenase (LDH), Beta-2 microglobulin, prothrombin time (PT/INR), partial thromboplastin time (PTT), hemoglobin A1c, and urine analysis, and a fasting serum glucose, triglycerides, cholesterol panel, and serum Beta-HCG in women of child-bearing potential. Fasting is defined as nothing to eat for at least 4-6 hours before blood draw.

ECHO or MUGA performed.

Quantitative immunoglobulins (IgG, IgA, and IgM) within 28 days prior to the first dose of TAK228.

HIV 1 and 2 antibody, Hepatitis C viral antibody, Hepatitis B surface antigen, Hepatitis B core antibody within 28 days prior to the first dose of TAK228.

The following staging studies should be performed within 28 days prior to the first dose of TAK228 – CT scans of neck, chest, abdomen, and pelvis; Chest X-ray – PA and lateral; and unilateral bone marrow biopsy and unilateral bone marrow aspirate. An optional PET/CT scan may be obtained within 28 days prior to the first dose of TAK228 at the discretion of the treating physician.

An electrocardiogram will be obtained within 28 days prior to the first dose of TAK228.

For correlative studies, an optional 10 ml of blood sample [2 heparin containing green top tubes (5 ml/tube)] will be collected within 3 business days prior to the first dose of TAK228. These samples will be transported within 4 hours of collection to the RPPA Core Laboratory Facility and/or Lymphoma Tissue Bank, depending on time of collection, at M. D. Anderson Cancer Center (MDACC). Blood from green top tubes will be processed for isolation of peripheral blood mononuclear cells (PBMC) using standard laboratory protocols.

For correlative studies, an optional archival tumor FFPE biopsy material collection will be occur for analysis of mutations in MTOR.

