For correlative studies, an optional biopsy will be collected within 28 days prior to the first dose of TAK228 for analysis of phosphorylation in mTOR and related proteins if the patient has a tumor deemed to be safely accessible by the treating physician.

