During the first cycle of TAK228, the following laboratory studies should be performed on day 15 (within 3 business days) - CBC with differential, Serum chemistries - Na, K, Cl, CO2, BUN, Cr, Ca, Mg, phosphorus, total protein, albumin, alkaline phosphatase, AST, ALT, total bilirubin, uric acid, and LDH, and a fasting serum glucose, triglycerides, cholesterol panel. Fasting is defined as nothing to eat for at

least 4-6 hours before blood draw.

Hemoglobin A1c should be obtained prior to cycle 1 day 1, cycle 3 day 1, cycle 6 day 1, cycle 9 days 1 and cycle 12 day 1.

An electrocardiogram will be obtained pre-dose (within 28 business days) prior to start of cycle 1 and within 3 days of starting each subsequent cycle.

The following staging studies should be performed at completion of 2 cycles of TAK228 (within 5 business days prior to starting cycle 3) – CT scans of neck, chest, abdomen, and pelvis; Chest X-ray – PA and lateral; and unilateral bone marrow biopsy and unilateral aspirate if bone marrow is involved with lymphoma at baseline. An optional PET/CT scan may be obtained at completion of 2 cycles of TAK228 at the discretion of the treating physician.

The following staging studies should be performed at completion of every 2 cycles beyond the first 2 cycles of TAK228 (i.e., +/- 5 business days prior to starting cycle 5, 7, 9, and 11): CT scans of neck, chest, abdomen, and pelvis; Chest X-ray – PA and lateral; and optional unilateral bone marrow biopsy and unilateral aspirate if bone marrow is involved with lymphoma at baseline at the discretion of the treating physician; An optional PET/CT scan may be obtained at completion of every 2 cycles of TAK228 at the discretion of the treating physician, but should be considered if previously FDG avid lymph nodes remain enlarged on CT imaging or physical examination.

In consenting patients, for correlative studies, a 10 ml of blood sample [1 heparin containing green top tube and 1 purple top tube (5 ml/tube)] will be collected at each of the following time points: cycle 1 day 1 (2-4 hours after dose), and cycle 2 day 1 (2-4 hours after dose). These samples will be transported within 4 hours (+/- 2 hours) of collection to the RPPA Core Laboratory Facility and/or Lymphoma Tissue Bank, depending on time of collection, at M. D. Anderson Cancer Center (MDACC). Blood from green top tubes will be processed for isolation of peripheral blood mononuclear cells (PBMC) using standard laboratory protocols.

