For correlative studies, an optional biopsy will be collected on day 14 (+/- 5 business days, within 4 hours of dosing) for analysis of phosphorylation of mTORC1/2 target proteins if the patient has a tumor deemed to be safely accessible by the treating physician and underwent Screening Biopsy.

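### The on-treatment biopsy window gives no direction or minimum delay relative to the dose, so the exploratory tumour phosphorylation change can mix near-trough and post-absorption samples

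*Combined protocol and SAP*

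**What the plan says.** The Exploratory Objectives include the change in phosphorylation of mTORC1/2 targets between baseline and "after therapy with TAK228 in optional pre- and post- therapy biopsy by utilizing reverse phase protein array". The baseline sample comes from Screening Evaluation: "an optional biopsy will be collected within 28 days prior to the first dose of TAK228". The on-treatment sample comes from Evaluation During Study: "an optional biopsy will be collected on day 14 (+/- 5 business days, within 4 hours of dosing) for analysis of phosphorylation". It applies only to patients who had the screening biopsy and whose tumour can be reached safely.

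The same section times the on-treatment correlative blood at "cycle 1 day 1 (2-4 hours after dose), and cycle 2 day 1 (2-4 hours after dose". The Rationale gives the purpose of the blood: "The peripheral blood mononuclear cells will be evaluated as a surrogate for mTORC1/2 inhibition and Akt phosphorylation after exposure to TAK228".

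On dosing, Proposed Treatment/Study Plan says "TAK228 milled API will be administered once daily at approximately the same time on each scheduled dosing day". The document supplied does not ask for the clock times of the dose and the biopsy to be recorded.

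**The concern.** Phosphorylation of a drug's targets may vary over the dosing interval. A limit of four hours around a dose, with no direction, can be met near the end of one interval or near the start of the next. Two schedulers could both follow the rule and take samples at very different times since the last effective dose.

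The matter at stake is whether the tumour objective can be interpreted. If a biopsy shows no fall in phosphorylation, the drug may not have inhibited its target in tumour, or the sample may have been taken when little drug effect was present. If clock times are not recorded, the analysis cannot separate the two afterwards. Each pair needs two optional biopsies and an accessible tumour. The document gives no expected number of pairs, so it cannot be assumed that timing differences will average out. The procedure is invasive and is done only for this analysis, which is a further reason to make each sample interpretable.

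**Working it through.** The plan states no sample size, precision or other figure for this endpoint, so there is nothing to reproduce. The check is interval arithmetic on the stated windows.

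**Inputs**
- Biopsy: within 4 h of dosing, direction not given (Evaluation During Study).
- Blood: 2 to 4 h after dose (Evaluation During Study).
- Dosing: once daily (Proposed Treatment/Study Plan), taken here as 24 h between doses on consecutive dosing days.

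**Does the wording elsewhere settle the direction?** It does not. In Screening Evaluation, "These samples will be transported within 4 hours of collection to the RPPA Core Laboratory Facility" can only mean after the event. In Evaluation During Study, the same construction, used with 3 business days and the first dose, describes the visit held before treatment starts. The objective's reference to post-therapy biopsy means after therapy has begun and does not fix the hour relative to that day's dose.

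**Two-sided reading (4 h before to 4 h after)**
- Time since the previous dose for a pre-dose biopsy: 24 − 4 = 20 h up to 24 h.
- Time since the current dose for a post-dose biopsy: 0 to 4 h.
- Overlap with the blood window: (4 − 2) / (4 + 4) = 2/8 = 25%.

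**After-dose-only reading (0 to 4 h)**
- Overlap: (4 − 2) / 4 = 2/4 = 50%.
- The other half, 0 to 2 h, is excluded for blood but allowed for the biopsy. A biopsy minutes after the dose is about 24 h after the previous one. An oral dose can plausibly have had little effect by then, so such a sample is close to a trough sample.

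**How much could it matter?** The document gives no half-life, time to peak or duration of effect. As an illustration only, suppose the effect decays exponentially with half-life h after a peak at about 2 h. The effect at 22 h relative to 3 h is then 2^(−(22 − 3)/h) = 2^(−19/h):

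| Assumed h (hours) | Effect at 22 h as a share of that at 3 h |
|---|---|
| 4 | 4% |
| 8 | 19% |
| 12 | 33% |
| 24 | 58% |
| 48 | 76% |

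The range runs from almost complete loss of effect to a modest loss. It shows that the document cannot fix the size, and it is not an estimate for TAK228.

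**Sampling days.** Day 14 with 5 business days either side spans, at its widest, days 7 to 21 of cycle 1. The on-treatment blood is drawn on day 1 of cycles 1 and 2, so on-treatment tumour and blood fall on different days whatever the hour.

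**The case against.** The strongest reply is that four hours of dosing is naturally read as four hours after it, so no pre-dose sample is allowed. That reading is reasonable, and if it is intended the 20 to 24 h samples drop out. It does not remove the problem, because there is still no minimum delay.

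A reader might go further and infer that the tumour data will mix opposite ends of the dosing interval and cannot be compared with the blood. The document does not support that. Mixing is permitted but not certain, and the windows overlap on either reading. No tumour-versus-blood analysis is planned: the two changes are separate exploratory objectives, and neither Analysis Plan nor Efficacy Analysis links them. The Rationale calls the blood cells a surrogate for target inhibition and does not propose to validate them against tumour. The lack of a blood tube on the biopsy day is therefore not a fault in a stated analysis. At baseline the two samples can share a day, since the screening biopsy may be taken in the 28 days before the first dose and the blood is taken in the last 3 business days before it.

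A reader might also attach a fold-range in drug exposure to the biopsy window. That would rest on assumed half-lives and would describe plasma concentration, whereas the endpoint is phosphorylation in tumour. Nothing in the document connects the two, so it cannot be claimed that timing variation exceeds the drug effect.

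Finally, the biopsy is optional and exploratory. That is correct, and it limits the weight of the point.

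**Conclusion.** The point holds in limited form. As written, the biopsy window lacks a direction and a minimum delay, and on either reading it admits samples that may be close to trough alongside samples taken up to 4 h after the dose. The arithmetic assumes a 24 h dosing interval. Treating a biopsy minutes after the dose as near trough further assumes that an oral dose needs some time to act. The effect on the phosphorylation result could be small if inhibition lasts long, or large if it is short-lived. The damage is confined to one optional exploratory objective. A cheap wording change before biopsies are taken is justified, and nothing here calls the trial's main conclusions into question.

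**What to change.** In Evaluation During Study, change the on-treatment biopsy window to 2 to 4 hours after dose, the window the plan already uses for the correlative blood. Require the clock times of that day's dose and of the biopsy to be recorded, so that any departure can be seen and allowed for in the analysis.

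The cost is a tighter slot for the biopsy. No biopsy is added, and the day window can stay as it is.

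A blood tube for mononuclear cells at the biopsy visit is an optional extra, useful if tumour and blood are to be read together. It should be additional: moving the cycle 2 day 1 tube would lose an existing time point. Sharing the cycle 1 day 15 laboratory draw is not free either. That draw includes fasting tests, so taking it 2 to 4 hours after the dose would extend the fast beyond the 1 hour the plan requires after dosing. Its window (3 business days around day 15) also differs from the biopsy's, so the two visits will not always coincide.

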#### **Evaluation At Completion of Study**

Patients will be evaluated by the treating physician and a relevant history and physical examination, including performance status evaluation and vital signs, will be recorded 1 week (+/- 7 business days) after completion of TAK228. Toxicities will be graded according to the NCI CTC v4.0 during this visit.

The following laboratory studies should be performed 1 week (+/- 7 business days) after completion of TAK228 – CBC with differential, Serum chemistries - Na, K, Cl, Glucose, CO2, BUN, Cr, Ca, Mg, phosphorus, total protein, albumin, alkaline phosphatase, AST, ALT, total bilirubin, PT/PTT/INR, urinalysis, uric acid, LDH, and quantitative immunoglobulins, and a fasting serum glucose, triglycerides, and cholesterol panel. In addition, an EKG should be performed 1 week (+/- 7 business days) after completion of TAK228. Fasting is defined as nothing to eat for at least 4-6 hours before blood draw.

The following staging studies should be performed 2 weeks (+/- 14 business days) after completion of TAK228 – CT scans of neck, chest, abdomen, and pelvis; Chest X-ray – PA and lateral; and optional bilateral bone marrow biopsy and unilateral aspirate if bone marrow is involved with lymphoma at baseline at the discretion of the treating physician. An optional PET/CT may be performed 2 weeks (+/- 14 working/business days) after completion of TAK228 at the discretion of the treating physician.

For correlative studies, 10 ml of blood sample [2 heparin containing green top tubes (5ml/tube)] will be collected when a patient is taken off study (+/- 14 business days). These samples will be transported within 6 hours of collection to the RPPA Core Laboratory Facility and/or Lymphoma Tissue Bank, depending on time of collection, at M. D. Anderson Cancer Center (MDACC). Blood from green top tubes will be processed for isolation of peripheral blood mononuclear cells (PBMC) using standard laboratory protocols.

Patients will be evaluated by the treating physician and a relevant history and physical examination, including performance status evaluation and vital signs, will be recorded 1 week (+/- 7 business days) after completion of TAK228. Toxicities will be graded according to the NCI CTC v4.0 during this visit.

The following laboratory studies should be performed 1 week (+/- 7 business days) after completion of TAK228 – CBC with differential, Serum chemistries - Na, K, Cl, Glucose, CO2, BUN, Cr, Ca, Mg, phosphorus, total protein, albumin, alkaline phosphatase, AST, ALT, total bilirubin, PT/PTT/INR, urinalysis, uric acid, LDH, and quantitative immunoglobulins, and a fasting serum glucose, triglycerides, and cholesterol panel. In addition, an EKG should be performed 1 week (+/- 7 business days) after completion of TAK228.

The following staging studies should be performed 2 weeks (+/- 14 business days) after completion of TAK228 – CT scans of neck, chest, abdomen, and pelvis; Chest X-ray – PA and lateral; and optional bilateral bone marrow biopsy and unilateral aspirate if bone marrow is involved with lymphoma at baseline at the discretion of the treating physician. An optional PET/CT may be performed 2 weeks (+/- 14 working/business days) after completion of TAK228 at the discretion of the treating physician.

For correlative studies, 10 ml of blood sample [2 heparin containing green top tubes (5ml/tube)] will be collected when a patient is taken off study (+/- 14 business days). These samples will be transported within 6 hours of collection to the RPPA Core Laboratory Facility and/or Lymphoma Tissue Bank, depending on time of collection, at M. D. Anderson Cancer Center (MDACC). Blood from green top tubes will be processed for isolation of peripheral blood mononuclear cells (PBMC) using standard laboratory protocols.

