Patients will be monitored by a cohort size of 5 after the first 15 patients according to the following stopping boundaries for OR at two cycles and reason for dose modification at one cycle. If the number of responses required for moving the trial to next stage has not been achieved, the patient enrollment will be halted until enough responses observed.

For cohorts I), TAK228 will be considered promising if it yields an OR rate of 45% at two cycles and a REASON FOR DOSE MODIFICATION rate of 25% at one cycle. A sample size of 25 ensures that, if the cohort is not terminated early, a posterior 90% credibility interval for overall response rate will have width of 0.310 at most, under the assumption of a 45% of OR rate. The prior probabilities of OR and REASON FOR DOSE MODIFICATION for the experimental regimen are modeled by beta distributions ( $Beta(0.9,1.1)$  and  $Beta(0.5,1.5)$ , respectively). Denoting probabilities of OR rate and REASON FOR DOSE MODIFICATION rate by ( $p_{OR}$ ,  $p_{Reason\ for\ dose\ modification}$ ), the following decision criteria will be applied: Stop the trial if  $Prob(p_{OR} < 45\% \mid data) > 0.95$  or  $Prob(p_{Reason\ for\ dose\ modification} > 25\% \mid data) > 0.95$ .

Patients will be monitored by a cohort size of 5 after the first 15 patients according to the following stopping boundaries for OR at two cycles and REASON FOR DOSE MODIFICATION at one cycle. If the number of responses required for moving the trial to next stage has not been achieved, the patient enrollment will be halted until enough responses observed.

Patients who are treated on study and have at least 1 disease restaging study prior to termination of study participation will not be replaced with an additional patient added to their disease cohort. Patients who are treated on study and fail to have at least 1 disease restaging study prior to termination of study participation will be replaced with an additional patient added to their disease cohort at the discretion of the principle investigator.

The duration of the study as a whole is defined first patient to start the screening period to the last patient to conclude their therapeutic period. The anticipated accrual is 3 patients per month on this trial. Thus, accrual for the study is expected to be complete in approximately two years. The total duration of the study is anticipated to be approximately three years.

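### The end-of-treatment safety visit has a tolerance wider than its own offset, so a compliant visit can give no toxicity observation after the last dose

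*Combined protocol and SAP*

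**What the plan says.** All references are to the combined protocol and SAP.

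- **Examination and toxicity grading.** Evaluation At Completion of Study has history, examination, performance status and vital signs that "will be recorded 1 week (+/- 7 business days) after completion of TAK228". It adds: "Toxicities will be graded according to the NCI CTC v4.0 during this visit".
- **Laboratory tests and EKG.** The window is the same: "The following laboratory studies should be performed 1 week (+/- 7 business days) after completion of TAK228" and "an EKG should be performed 1 week (+/- 7 business days) after completion of TAK228".
- **Other end-of-treatment items.** Staging is at 2 weeks (+/- 14 business days). A correlative blood sample "will be collected when a patient is taken off study (+/- 14 business days)". Toxicity grading is listed for neither.
- **Duplicate text.** The section is printed twice with the same windows. This is one visit described twice, not two visits.
- **On-treatment grading.** Evaluation During Study grades toxicity before the start of treatment, on days 8, 15 and 22 of cycle 1, and then before each later cycle, with a tolerance of 3 business days. Cycles last 28 days. Safety Analysis also has patients asked about toxicities at each cycle visit.
- **Use of the data.** Safety and tolerability is a secondary objective. Population for Analysis puts every patient who receives any study drug into the safety analyses.

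The supplied text gives no minimum interval between the last dose and this visit, no later toxicity visit and no adverse event follow-up period after the last dose.

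**The concern.** A post-treatment safety visit exists to observe the patient for some time after dosing has stopped. Here the permitted deviation is larger than the interval itself, so the schedule does not secure any such time. The visit can coincide with the last on-treatment contact and still be within window. Examination, grading, laboratory tests and EKG share the window, so all four can fall there together.

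At stake is the completeness of the safety data after the last dose. Three things could go unrecorded: toxicity that first appears after an early visit, toxicity that worsens after it, and the later course of toxicity still unresolved at it. The length of post-treatment observation would also differ from patient to patient through scheduling alone. That adds noise to the toxicity frequency tables and to the planned logistic regression of toxicity on prognostic factors.

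**Working it through.** The plan gives no figure to reproduce. The check is calendar arithmetic.

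**Inputs**
- Offset: 1 week = 7 calendar days = 5 business days (Evaluation At Completion of Study).
- Tolerance: 7 business days either side (same section).
- Assumption: business days are Monday to Friday, with public holidays ignored.
- Day 0 is the day of the last dose.

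**Formula**
- Target = day 0 + 7 calendar days, which is the same weekday one week later.
- Opening = target - 7 business days. Five of these return to day 0, so the opening lies 2 business days before the last dose.
- Closing = target + 7 business days. Five of these reach day 14, so the closing lies 2 business days after day 14.

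**Results for a weekday last dose**

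| Last dose | Opens | Closes | Span (days) |
|---|---|---|---|
| Monday | -4 | +16 | 20 |
| Tuesday | -4 | +16 | 20 |
| Wednesday | -2 | +16 | 18 |
| Thursday | -2 | +18 | 20 |
| Friday | -2 | +18 | 20 |

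Example, Monday: two business days before a Monday is the preceding Thursday, day -4. Two business days after the Monday on day 14 is Wednesday, day 16. A weekend last dose, with the target rolled to the nearest business day inside the window, opens on day -2 or -3 and closes on day +17 or +16.

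**More lenient readings**
- Business days read as calendar days: 7 - 7 = 0 and 7 + 7 = 14, so day 0 to day +14.
- Completion of TAK228 read as a floor: day 0 to day +16 or +18.

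Both still admit a visit on the day of the last dose.

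**What a narrower early side would do**
- -5 business days: opens on day 0 for any Monday-to-Friday last dose, so the fault remains.
- -3 business days, the on-study tolerance: opens on day +2 (Monday, Tuesday or Wednesday last dose) or day +4 (Thursday or Friday). A weekend last dose opens on day +4 (Saturday) or +3 (Sunday).

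**Does anything else supply post-treatment grading?** The staging and blood-sample items list none. The on-treatment visits precede or accompany dosing. From cycle 2 they occur once per 28-day cycle, so for a patient who stops mid-cycle the completion visit may be the only scheduled grading since that cycle began.

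**The case against.** The strongest reply is that the visit is described as following completion of TAK228, under a heading about completion, so a visit before the last dose is not what was meant. That is a fair reading and it weakens the negative days. It does not remove the point, because a day-0 visit remains within window and no minimum interval is stated.

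A second reply is that the supplied text is abstract-style, and an adverse event reporting period may be set elsewhere. This cannot be excluded. The finding is limited to the supplied text.

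Four stronger readings are tempting, and the documents do not support them.

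- **Toxicity that causes a patient to stop is never graded.** Such toxicity is present on treatment, where it is asked about and graded at cycle visits, and a day-0 completion visit would grade it too. Only its later course can be missed.
- **Every patient has a window from day -4 to day +18.** Those limits belong to different weekdays of last dose. No single patient's window exceeds 20 days.
- **The study closes before the last patient's visit is due.** Phase II design runs the study "to the last patient to conclude their therapeutic period". That sentence defines overall duration for planning and cancels no visit required elsewhere.
- **The staging window needs the same repair.** It reads "The following staging studies should be performed 2 weeks (+/- 14 business days) after completion of TAK228", and it too exceeds its offset. But staging is not a toxicity assessment, and barring an early scan could force a repeat CT in a patient just scanned on treatment.

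It is also true that this is a single-centre, non-randomised trial. The primary endpoint is response, and the toxicity stopping rule uses dose modification at one cycle. Neither depends on this visit.

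**Conclusion.** The point holds as a wording defect in the timing of one safety visit. The schedule permits between 0 and 16 to 18 days of observation after the last dose, and a visit giving none is compliant on the literal, calendar-day and floor readings alike. It applies to every treated patient, up to 75.

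It affects the secondary safety objective only. The conclusion is about what the window allows. The documents do not show how many visits would be held early, so the amount of toxicity lost cannot be estimated. It rests on a Monday-to-Friday working week without holidays, and on there being no adverse event follow-up period outside the supplied text. The change is worth making because it is definite and cheap.

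**What to change.** In Evaluation At Completion of Study, keep the visit and give its early side a floor after the last dose, for example 1 week (-3/+7 business days) after completion of TAK228. The 3 business days are the tolerance already used for on-study visits. The window would then open 2 to 4 days after the last dose, and its late limit would stay at day +16 to +18.

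Apply the same wording to the examination, toxicity grading, laboratory tests and EKG, in both printings of the text, or delete the duplicate printing. If an adverse event follow-up period exists in another document, cite it here.

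Cost: a wording change, with no new visit or procedure. The visit can no longer be merged with the last on-treatment visit, and a few more visits may be counted as deviations.
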